Methods: Consented participants receiving TAU for PTSD at LRTC will be randomized to receive 20 consecutive days of adjunct iTMS according to one of these two treatment arms: **Arm 1** TAU plus iTMS to the right DLPFC or **Arm 2** TAU plus sham iTMS to the right DLPFC. At UTHSCSA's Research Imaging Institute (RII), where all brain imaging and motor threshold assessments will be conducted, iTMS treatment plans will be generated based on (pre-treatment) anatomical and functional magnetic resonance imaging (fMRI) to guide the optimal robotic positioning of the TMS coil to accurately target each subject DLPFC. Participants will be assessed at baseline, during treatment, immediately following treatment and at 1-month post-treatment. A comparison of baseline brain connectivity measurements with subjects' fMRI conducted immediately following treatment will be conducted to identify network connectivity changes potentially associated to treatment response.

Clinical Relevance: This will be the first study to determine the clinical effects of adjunct iTMS delivered to the right DLPFC in the treatment of PTSD, to provide clues about the ideal neural networks to target for more robust clinical outcomes, and to identify potential biomarkers of treatment response including changes in brain networks connectivity.

Item 3 Background	
--------------------------	--

Describe past experimental and/or clinical findings leading to the formulation of your study.

For research involving unapproved drugs, describe animal and human studies.

For research that involves approved drugs or devices, describe the FDA approved uses of this drug/device in relation to your protocol.

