

Item 4 Purpose and rationale Insert purpose, objectives and research questions/hypotheses here. If you cut and paste from another document, make sure the excerpted material answers the question
	
We propose a randomized, double-blind, sham-controlled, 20 consecutive day trial of adjunct TMS to the right DLPFC in active duty service members and veterans with PTSD receiving an integrated and evidence-based treatment (i.e. TAU) for PTSD incorporating both adequate pharmacological approaches and Cognitive behavioral therapy (CBT) at Laurel Ridge Treatment Center (LRTC). In addition to TAU, consented patients will be randomized to receive irTMS in one of two treatment arms: Arm 1 delivers active irTMS to the right DLPFC. Arm 2 delivers sham TMS (inactive coil) to the right DLPFC. To ensure equivalent placebo effects across arms, sham TMS delivers the exact sound produced during active irTMS, therefore patients are unable to discriminate between sham and active TMS. Moreover, clinicians providing TAU at LRTC and researchers conducting clinical outcomes assessments will be blinded to each participants' treatment arm. Resting-state fMRIs (rs-fMRIs) will be used both for treatment planning (baseline imaging), which guides the individualized positioning of the TMS coil, and to characterize TMS-induced network connectivity (imaging treatment week 3). Self-report scales will be done weekly at LRTC. A 1-month post-treatment clinical follow-up will be conducted in person or over the phone to evaluate maintenance of clinical outcomes. Considering that depressive symptomatology, often meeting diagnostic criteria Major Depressive Disorder (MDD), is commonly observed in patients with PTSD, patients with comorbid PTSD and MDD won't be excluded from the study and we will also assess depressive symptoms throughout treatment at the same time intervals—i.e., baseline, weekly, and 1 month post-treatment.
 
Aim 1. Test whether compared with TAU plus sham irTMS, TAU plus adjunct active irTMS is associated with greater clinical improvement that differs in specificity to PTSD or depressive symptomatology according to the targeting of right DLPFC .
 
 Hypothesis 1. TAU plus adjunct active irTMS to the right DLPFC will be superior to TAU plus sham irTMS in relieving PTSD symptoms. 
Aim 2. Test for irTMS-induced changes in network functionality (plasticity) using rs-fMRI.
 
 Hypothesis 2a. Intrinsic connectivity will be attenuated by active irTMS in networks connected to the respective treatment sites, as tested by correlation with the number of sessions received at the time of scanning and by pre-treatment-to-post-treatment contrast. Hypothesis 2b. Treatment-induced decreases in connectivity will correlate with symptom improvement within and across treatment arms.

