Step-by-Step Methods: We propose to test 100 patients (i.e. 50 per arm) who meet criteria for PTSD as determined by the Clinician Administered PTSD Scale (CAPS-5) and the outlined study inclusion criteria. We anticipate consenting and screening approximately 200 male and female subjects, in order to meet the target enrollment goals. To account for subject dropouts and retain a sample of 100 subjects completing the double-blind treatment phase (50 per treatment group), 132 eligible subjects (66 in each group) meeting the study inclusion criteria will be randomized for the study. See also Table of Study Procedures below.

Recruitment

Patients will be recruited at LRTC from institution's PTSD inpatient program by the study staff supervised by the On-site Investigator's team. Upon admission to the LRTC, patients will be informed about this treatment trial by either their staff psychiatrist or a member of the LRTC's research team. Each patient will be given an information sheet describing the study. If interested in participating, each patient will be shown a video describing the treatment trial and each of the tools/treatments used throughout the study (i.e. MRI and TMS).

Pre-Screening and LRTC Intake

Under an IRB approved HIPAA Waiver of Authorization, Waiver of Informed Consent, and Waiver of Documentation of Informed Consent, study personnel will conduct a brief pre-screening intake interview where the basic study inclusion and exclusion criteria will be reviewed to help the individual determine if he or she meets the study criteria or has obvious exclusions from the study protocol. This information will be maintained as a secure file with the following information: name, phone number, name of study, referral date, referral source, potential eligibility status, reason if not eligible, and verbal permission to contact the caller in the future for other studies. Subjects who agree to study participation will sign a consent document before any further screening will take place. Any individually identifiable information and Protected Health Information (PHI) collected on individuals who do not consent to participation will not become part of the research data. If subjects agree to participate in the research, the identifiable data collected will become part of the subjects' research records and will be stored according to the research confidentiality plan.

Consent Process

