robust and widely used pulse sequence for intrinsic connectivity modeling. BOLD images will be used for computing treatment plans and for testing for intrinsic connectivity changes by symptom score and with treatment. BOLD data will be acquired as 360 whole-brain volumes acquired with a TR = 2500 ms, TE = 30 ms, tip angle = 90°, 128 x 128 voxels, 1.7 mm x 1.7 mm, and 36 slices (4.0 mm thickness). This sequence requires ~ 15 minutes. Resting-state BOLD (15-min acquisition) will be used to map per-subject the voxel-wise intrinsic connectivity of DLPFC with the anterior cingulate cortex (ACC) and Precuneus; this will guide aiming parameters.

Motor Threshold Assessment. After the baseline MRI session, each patient will undergo a brief motor threshold assessment by single pulse TMS to their primary motor cortex hand region which elicits a contraction of the targeted hand muscle. The motor threshold assessment begins by locating the hand region and applying single pulses of TMS—with at least 5 seconds between successive pulses—at increasing levels of TMS intensity. We continue to ramp up the TMS intensity with each TMS pulse until we observe a contraction of the targeted hand muscle in 5 out of 10 pulses at a given TMS intensity. This TMS intensity will then be recorded as that patient's resting motor threshold. Using the patient's BOLD fMRI of the primary motor cortex, we can calculate their coil-to-cortex depth and use this information to determine the correct irTMS treatment intensity for the DLPFC and also determine the correct train duration needed to safely deliver 20Hz irTMS in each patient using published safety guidelines on appropriate train durations at specific TMS frequencies and intensities.

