The right DLPFC treatment target locations will be based on connectivity strength with ACC and Precuneus using region-seeded resting-state BOLD fMRI. Coil orientation will be corrected for the underlying gyral anatomy, using a T1-MRI derived cortical surface model to align the E-field according to the cortical column cosine model. Stimulation intensity will be corrected for the distance of the stimulation site from the scalp/coil surfaces. Intensity ranges will be individually adjusted for each patient—to deliver depth-corrected E-fields between 80 volts/meter and 95 volts/meter.

Sham TMS: An image-guided treatment plan will be computed for sham TMS subjects in the same manner as for active irTMS to ensure therapist blinding.

irTMS Treatment Sessions. All participants will continue with their TAU at LRTC (or its treatment clinics) including regular medication management encounters with their attending psychiatrist and therapy sessions as of their treatment. An effort will be made to limit the disruptions in patients' TAU by working research assessments and irTMS around their expected TAU programming. irTMS treatment visits will take place at the LRTC starting as soon as possible after the treatment plan is completed, expected to be 1-2 working days following baseline scanning.

irTMS Position/Holding. For each subject, the coil pose will be pre-computed from structural and functional MRI and stored as an individualized treatment plan. Each subject's treatment plan will be registered to his/her head by creating a scalp model with a high-resolution digitizer, an integrated component of the irTMS system. In each arm,

the TMS coil will be positioned and held by the robot (under the treatment technician's supervision).

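### Hypothesis 2a credits active irTMS with a fall in connectivity, but neither of its stated tests compares active with sham

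*Combined protocol and SAP*

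**What the plan says.** Item 4, Aim 2, Hypothesis 2a states a causal claim, that active irTMS will lower intrinsic connectivity in the networks of the treated site, "as tested by correlation with the number of sessions received at the time of scanning and by pre-treatment-to-post-treatment contrast". The abstract (Item 2, Methods) describes the imaging comparison in the same within-patient way: "A comparison of baseline brain connectivity measurements with subjects' fMRI conducted immediately following treatment will be conducted to identify network connectivity changes". The Neuroimaging Data Analysis Plan in Item 6 (Intrinsic Connectivity by BOLD fMRI) likewise refers only to differences between each patient's two scans.

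Elsewhere the comparator is named. Hypothesis 1, in the same item, says that active treatment "will be superior to TAU plus sham irTMS in relieving" PTSD symptoms. The mixed effects models appear under the Clinical Outcomes Data Analysis plan, with the PCL-5 and CAPS-5. Hypothesis 2b mentions both arms, but it concerns the correlation of connectivity change with symptom change, not a difference between arms in connectivity change.

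**The concern.** Item 6 (irTMS Treatment Sessions) states "All participants will continue with their TAU at LRTC", so medication and psychotherapy run in both arms between the two scans. A pre-post change in the active arm therefore mixes irTMS with TAU and the passage of time. Followed as written, Aim 2 could report irTMS-induced plasticity when active and sham change equally. It could also miss a real attenuation hidden by a rise common to both arms.

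The session correlation is not a stated substitute. Session counts are capped at 20 and depend partly on length of stay (irTMS Treatment Protocol). They can also vary through missed sessions or through a scan taken before the last session. Sham patients attend sessions too. The correlation would act as an arm comparison only if they were coded as zero active sessions, which the documents do not say.

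The sham arm could settle the matter: "An image-guided treatment plan will be computed for sham TMS subjects in the same manner as for active irTMS", and the post-treatment scan is scheduled without distinction by arm.

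**Working it through.** **Text.** The sections cited above were set side by side. None states an active-versus-sham contrast of connectivity change.

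**Inputs.** The plan gives no power calculation for Aim 2, so there is no figure to reproduce. From the documents: 50 completers per arm (Item 6, Step-by-Step Methods). Assumed: two-sided 5%; one connectivity measure with baseline SD 1 at both scans; test-retest reliability r = 0.5, 0.7 or 0.9; a shared shift of 0.1 to 0.3 baseline SD. The documents do not say that TAU changes connectivity, or in which direction.

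**Pre-post test, active arm only.** SD of change = √(2(1 − r)) = 1.000, 0.775, 0.447. Dividing by √50 gives SE = 0.141, 0.110, 0.063. With a shared fall of 0.2 and no irTMS effect, the noncentrality is 0.2/SE = 1.41, 1.83, 3.16 on 49 df. The chance of a significant fall is:

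| Shared fall (baseline SD) | r = 0.5 | r = 0.7 | r = 0.9 |
|---|---|---|---|
| 0.1 | 10% | 14% | 34% |
| 0.2 | 28% | 43% | 87% |
| 0.3 | 55% | 77% | 99.6% |

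Pooling the two arms makes this worse. At r = 0.5, where the SD of change equals the baseline SD, n = 100 gives 51% at 0.2 and 84% at 0.3.

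**Between-arm test** (post-treatment value regressed on arm and baseline). SE = √(2(1 − r²)/50) = 0.173, 0.143, 0.087 on 97 df. A shared change cancels. In 20,000 simulated trials per setting, with shared falls of 0 to 0.3 SD, the false-positive rate was 4.8–5.1% two-sided and 2.3–2.5% in the attenuation direction.

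**Masking.** Suppose irTMS truly lowers connectivity by 0.4 SD. With no shared change, the pre-post test detects it in 79%, 95% and 100% of trials. With a shared rise of 0.2 the net fall is 0.4 − 0.2 = 0.2, and detection drops to 28%, 43% and 87%. The between-arm test gives 63%, 79% and 99.5% either way.

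**Session correlation.** This was simulated with 20,000 trials, a shared fall of 0.2 SD and a true dose-linear fall reaching 0.5 SD at 20 sessions. The session spreads are assumed.

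| Spread of sessions | Power, active arm only | Power, sham coded as zero (r = 0.5 / 0.7 / 0.9) |
|---|---|---|
| 70% at 20, the rest 16–19 | 4–7% | 67% / 87% / 99.9% |
| Even over 10–20 | 8–23% | 49% / 71% / 99% |

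Within the active arm the weakness is low power, not false positives. Even if a TAU fall is proportional to sessions (0.2 SD at 20), false attenuation is only 3–7%. With sham coded as zero, false positives are about 5% two-sided.

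**Caveat.** Baseline scans also choose the target: "The right DLPFC treatment target locations will be based on connectivity strength with ACC and Precuneus using region-seeded resting-state BOLD fMRI". Regression to the mean in the selected connections is therefore possible, in a direction that depends on a selection rule the documents do not state. The sham arm carries the same effect, so an arm comparison also deals with this.

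**The case against.** The strongest reply is that the trial is randomised and sham-controlled, both arms are scanned, and the hypothesis concerns active irTMS. A pre-post contrast may simply name the measure of change, which a sensible analyst would then compare between arms. That is a fair reading, but the hypothesis says how it will be tested and the comparison is not there. The choice between an active-arm, pooled or between-arm contrast is left open until after unblinding.

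A second reply is that the two tests are joined by an "and". If both must be significant within the active arm, joint false attenuation at a shared fall of 0.2 SD is under 5% in the settings tried, far below 28–87%. That is correct, but the plan states no such rule. Under it, the low power of the session correlation would make a true effect very hard to confirm. If baseline scans entered that correlation as zero sessions, it would become nearly the pre-post contrast, with the same weakness.

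Two further points stand. Every rate above rests on assumed shifts, reliabilities and session spreads for a single measure, while the imaging plan describes voxel-wise seed correlations; any multiplicity control would move the numbers. The plan also defines no single summary of the treated network, which any between-arm model needs.

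**Conclusion.** The concern holds as a matter of text: the documents state no active-versus-sham test of connectivity change, and the tests they do state cannot attribute a change to irTMS. How often this would mislead is not known. On the stated assumptions, a shared fall of 0.1 to 0.3 baseline SD gives a false attenuation in 10% to 99.6% of trials by the active-arm pre-post test taken alone, against about 2.5% for the arm comparison. The consequence is confined to the mechanistic Aim 2. The primary clinical conclusion is untouched. The point should be fixed, since the remedy uses data already planned.

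**What to change.** Before unblinding, state that the main test of Hypothesis 2a is the active-versus-sham difference in post-treatment connectivity of the treated-site network, by linear regression on arm and baseline connectivity. Name the connectivity measure: the targeting text refers to ACC and Precuneus, the analysis text to DLPFC-limbic and DLPFC-motor networks. Keep the within-arm pre-post contrast as descriptive and the session correlation as exploratory, and say how sham sessions are coded in it.

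This changes the analysis text only; both scans are already scheduled in both arms. The cost is precision. The SE ratio to the one-arm test is √(1 + r) = 1.22, 1.30, 1.38. The effect detectable with 80% power rises from 0.40 to 0.49, from 0.31 to 0.40 and from 0.18 to 0.25 baseline SD at r = 0.5, 0.7 and 0.9.

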Phase I: Baseline MRI. Once the participant has completed the psychological assessments required to determine inclusion/exclusion criteria, eligible participants will be taken from the LRTC to the Research Imaging Institute (RII) at UTHSCSA. When the participant arrives, the participant will undergo an anatomical and functional magnetic resonance imaging (MRI) session. Earplugs will be provided at every MRI session. MRIs use strong magnets and radio waves to non-invasively acquire images of organs and tissues. Unlike X-rays, MRIs do not expose subjects to radiation, therefore it is considered safe to obtain many MRIs in a single scanning session or over multiple days; the initial MRI scans may take up to 2 hours. In the event that the participant cannot tolerate the MRI procedure, they will be withdrawn from the study. Participants will be imaged at the RII using a research-dedicated 3T Siemens TIM/Trio MRI scanner (Siemens, Erlangen, Germany) with an eight-channel phased array coil. Structural imaging will be obtained only once, upon enrollment. Structural images will be used for iTMS treatment planning (described below) and for spatial normalization to a standard anatomical template. MRI images will be obtained two times (i.e. pre-treatment and post-treatment) and used to detect symptom-specific network abnormalities and treatment-induced plasticity. We will also perform motor threshold assessments for each patient (at pre-treatment and post-treatment, immediately after each MRI) to determine the correct intensity and train durations needed to safely deliver iTMS in each patient's 3-Week Treatment Phase. The post-treatment motor threshold assessment are important to the future establishment of safety guidelines for iTMS treatment of PTSD.

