TMS treatment guidelines recommend that the train duration of TMS pulse protocols remain within the limits of published safety guidelines (reached by a consensus of TMS practitioners). For example, if a patient requires a TMS intensity equivalent to 130% of their motor threshold, then we must limit our TMS train durations to 0.55 seconds (i.e. 11 pulses/train). Therefore, we will adjust the train duration of each patient's treatment protocol so that it falls within the limits of these recommendations. We will also adjust the intertrain interval to ensure that we deliver all of our treatment pulses within the hour-long treatment session. For example, if a patient needs a TMS intensity equivalent to 130% of their resting motor threshold, we will deliver 160 pulse trains of irTMS (e.g. train duration = 0.5 seconds; intertrain interval = 7.5 seconds; 10 pulses per train), which would require 21.33 minutes of treatment time to deliver the desired number of TMS pulses in each session (i.e. 1,600 pulses). The primary TMS treatment parameters (TMS frequency (i.e. 20Hz), number of pulses per session (i.e. 1,600), and number of sessions (i.e. 20) will remain the same across patients. We may only adjust the patient's intensity and the protocol's train duration and intertrain intervals so that they fall within the safety limits of repetitive TMS treatments.

Active treatment will use a liquid cooled figure-8 MagPro coil (MagVenture, Denmark). Sham treatment will use a coil that simulates the sound and scalp stimulation of TMS but does not deliver an E field (MagVenture, Denmark).

Participants will receive treatment 7 days per week for as long as they are hospitalized at LRTC for up to 20 sessions. On each treatment day, a total of 1,600 pulses will be administered within the one hour TMS session. With the set up for treatment, the total time required for each treatment visit should be less than one hour per day. This protocol will administer a total of 24,000 pulses over the three-week period. If study participants decide, at any time, that they cannot tolerate the irTMS treatments, they will be withdrawn from the study (see Discontinuation and Withdrawal of Patients Section below) and will be assisted in finding appropriate after-study care.

Phase II: Post-Treatment Follow-Up

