Post-treatment MRI. Immediately following the last irTMS treatment at the end of the 3rd week, a second functional MRI scan will be conducted to assess treatment effects. The post-MRI will occur any time after last treatment with up to a 3-day window for completion. In rare instances, if scheduling circumstances (such as weekends and institution holidays, MRI staff outages, participant discharge date) prevent the post-MRI from occurring after all treatment sessions have been completed, the post-MRI may be conducted before the final treatment session, and any remaining treatment sessions will occur after the post-MRI. This will be documented in the participant study file and will be considered during data analysis. After the post-treatment MRI session, each patient will also undergo another brief motor threshold assessment in order to document any changes which may be used to report on the safety of this TMS treatment protocol. This second scanning visit should take approximately 1 hour.

Participant Blind Form. The Participant Blind Form measures the participant's best guess about the study treatment that they received, level of confidence in this guess, and how unblinding could potentially have occurred. This form will be used at treatment completion and follow-up for all CAP RCTs that are double-blind (i.e., medication studies).

Independent Evaluator Blind Form. The Independent Evaluator Blind Form measures the independent evaluator's best guess about the study treatment that the subject received, level of confidence in this guess, and how unblinding could potentially have occurred.

Phase III: 1 Month/3 Month Follow-Up

One month and three months after the final iTMS treatment session, participants will be interviewed (either in-person or over the telephone) by a member of the research team. Self-report measures may be administered over the phone or by direct electronic data capture via a secure link to the secure STRONG STAR database.

Table of Study Procedures:

Phase	Pre-Study (at LRTC)			3 Week Treatment (at LRTC & the RII)			Post-Treatment (at the RII)	1 Month/3 Month Follow-Up (either in-person or via telephone)
	Wk 0			Wk 1	Wk 2	Wk 3	Wk 3	Wk 7/Wk15
	LRTC Intake	Baseline	MRI Appt					
	Day(s)	0 to 1	1-3	2-3	7	14	20	21 -24
Medical History	X							
Metal Screening		X						
Informed Consent		X						
1. Demographics & Military Service Characteristics		X						
2. History of Head Injuries Screening		X						

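### Hypothesis 2a relies partly on a correlation with session count, but with one scan before treatment and one after it, that correlation gives no interpretable dose-response

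*Combined protocol and SAP*

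**What the plan says.** Item 4, Aim 2, names two tests of Hypothesis 2a: "as tested by correlation with the number of sessions received at the time of scanning and by pre-treatment-to-post-treatment contrast". It places the outcome imaging at a single point, "to characterize TMS-induced network connectivity (imaging treatment week 3").

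Item 6 gives the scan schedule. Under Phase I: Baseline MRI, "MRI images will be obtained two times (i.e. pre-treatment and post-treatment"). Under Post-treatment MRI, "Immediately following the last irTMS treatment at the end of the 3rd week, a second functional MRI scan will be conducted". The Table of Study Procedures also marks connectivity imaging twice and shows no intermediate scan.

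On exposure, the irTMS Treatment Protocol says the "number of sessions (i.e. 20) will remain the same across patients". It also says "Participants will receive treatment 7 days per week for as long as they are hospitalized at LRTC for up to 20 sessions". In rare cases of scheduling difficulty, "the post-MRI may be conducted before the final treatment session, and any remaining treatment sessions will occur after the post-MRI"; such cases are to be documented and taken into account in the analysis, by a method not given. The Clinical Outcomes Data Analysis plan treats fewer than 16 sessions as non-compliance, to be evaluated.

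The imaging analysis plan (Data Analysis, Intrinsic Connectivity by BOLD fMRI) describes pre- versus post-treatment differences only. Session count does not appear in it.

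**The concern.** A correlation between connectivity and cumulative sessions tells the reader something about dose only if scans fall at different session counts, preferably by design. Here they fall in two clusters: none, and the end of the course. The test can be read in two ways, and Item 4 does not say which is meant.

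- **Both scans pooled.** Session count then mostly records whether the scan came before or after treatment. Anything else that changes over those three weeks, including usual treatment and the passage of time, moves with it.
- **Second scans only.** The predictor varies only because of length of stay, missed sessions and scan scheduling. None of these is assigned at random.

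What is at stake is the conclusion of Aim 2. A significant correlation would be counted as separate support for stimulation-induced plasticity. It could instead be the pre/post contrast reported a second time, or a pattern in who received fewer sessions.

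**Working it through.** The documents give no effect size, SD, alpha or power for Aim 2, so there is no stated figure to reproduce.

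**Inputs from the documents.** Two connectivity scans per participant; 0 sessions at the first; 20 planned sessions of 1,600 pulses; 50 completers per arm.

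**Assumptions.** The spread of sessions at the second scan; two-sided alpha 0.05; an effect linear in sessions; SD of connectivity change equal to 1.

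**1. Pooled reading.** Take equal numbers of first scans (0 sessions) and second scans (mean m, SD s). The variance of session count is (m/2)² + s²/2. The share that is simply pre versus post is (m/2)² / [(m/2)² + s²/2], and its square root is the correlation with the pre/post indicator. For sessions uniform on 16–20: m = 18, s² = 2, so 81/(81 + 1) = 0.988 and r = 0.994.

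| Assumed sessions at second scan | m | s | Share | r |
|---|---|---|---|---|
| 85% at 20, 8% at 19, 4% at 18, 3% at 16 | 19.72 | 0.80 | 0.997 | 0.998 |
| Uniform 16–20 | 18 | 1.41 | 0.988 | 0.994 |
| 60% at 20, 15% at 19, 10% at 18, 10% at 16, 5% at 12 | 18.85 | 2.01 | 0.978 | 0.989 |
| Uniform 10–20 | 15 | 3.16 | 0.918 | 0.958 |
| Uniform 1–20 (only if early stoppers are scanned) | 10.5 | 5.77 | 0.624 | 0.790 |

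A simulation (5,000 runs, 50 participants, sessions 16–20) compared a paired pre/post test with a within-person slope on session count. The two gave the same verdict in 97–99% of runs. With a step change of 0.4 SD and no dose effect at all, each was significant in 78.6% of runs. The slope cannot distinguish dose from before/after.

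**2. Second scans only.** Let the total effect over 20 sessions be d, so the slope is b = d/20. The expected correlation of change with session count is r = bs/√(1 + (bs)²), and power follows from Fisher's z with n = 50. For d = 0.8 and sessions 16–20: bs = 0.04 × 1.41 = 0.057, r = 0.056, power 6.7%. About 2,459 participants would be needed for 80% power.

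| Spread (d = 0.8) | r | Power, n = 50 |
|---|---|---|
| Uniform 16–20 | 0.056 | 6.7% |
| Uniform 15–20 | 0.068 | 7.5% |
| Uniform 10–20 | 0.125 | 13.9% |
| Uniform 1–20 | 0.225 | 34.8% |

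With d from 0.5 to 1.0 and sessions 16–20, power is 5.7% to 7.7%. The smallest r detectable with 80% power at n = 50 is 0.39.

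**3. Sensitivity to who gets fewer sessions.** In the same simulation with no dose effect, session count was linked to the participant's own connectivity change. At a latent correlation of 0.3 the post-scan correlation was falsely significant in 52% of runs; at 0.5, in 94%. These values are illustrative: the documents give no basis for the strength of any such link.

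**4. The planned exposure.** The irTMS Treatment Protocol gives 20 sessions of 1,600 pulses, which is 20 × 1,600 = 32,000. It also gives a total of 24,000 pulses, and 24,000/1,600 = 15 sessions. These statements must be reconciled. The argument does not depend on the answer: with counts uniform on 11–15, m = 13 and s² = 2, so 42.25/(42.25 + 1) = 0.977 and r = 0.988.

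**The case against.** The strongest reply is that the practical exposure is one phrase in a hypothesis statement. The imaging analysis plan and the abstract in Item 2 describe only a baseline-to-post comparison. Early second scans will be documented and considered, and non-compliance will be evaluated. The aim is mechanistic. All of this is true and limits the importance of the point. It does not remove it: Item 4 still names the correlation as a test of Hypothesis 2a, and no analysis section says how it would be done or interpreted.

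A reader might also infer more than the documents support:

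- *That no dose-response can be computed.* A coefficient can be computed. What is missing is an interpretation that separates dose from time, usual treatment or the reasons for a shortfall.
- *That the remaining spread is known to be driven by clinical course.* Session count is never randomised, but several of the listed scheduling reasons (holidays, weekends, scanner staffing) are logistical. Discharge date and missed sessions may be related to outcome; no passage says that they are.
- *That intolerance and worsening create the spread.* Participants who cannot tolerate treatment are to be withdrawn, and the Discontinuation of Subjects section covers assessments as well as treatment. Such participants may have no second scan. The documents do not say that early stoppers are scanned. If they were, the range would widen, but stopping is partly outcome-driven, so confounding could grow.
- *That a null result would be uninformative.* This applies to the second-scan-only reading. Under the pooled reading, a null says about as much as a null pre/post contrast.

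**Conclusion.** The point holds in this form: two scan times and a common planned session number leave the session-count correlation without an interpretable dose-response. Pooled, it duplicates the pre/post contrast (r between 0.989 and 0.998 under three assumed spreads with most participants near 20 sessions; 0.96 if counts run evenly from 10 to 20). Restricted to second scans, it has roughly 6% to 8% power for total effects of 0.5 to 1.0 SD with sessions 16–20, and it is open to bias of unknown size. These figures rest on assumed session distributions and a linear effect, because the documents give neither. That pooled session count cannot separate dose from time, and that second-scan counts are not randomised, follows from the scan schedule and does not depend on those assumptions. Hypothesis 2a as a whole remains testable, since the second scan supplies a change score in each arm. The PCL-5 and CAPS-5 outcomes are unaffected.

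**What to change.** In Item 4, Aim 2:

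- Remove the session-count correlation as a deciding test of Hypothesis 2a.
- Let the active-versus-sham difference in pre-to-post connectivity change decide it. This comparison is randomised and uses scans already scheduled for both arms. A pre/post contrast within the active arm alone also carries time and usual-treatment effects.
- Report the number of sessions at the second scan descriptively.
- If a session-connectivity association is still wanted, label it exploratory, restrict it to post-treatment scans in the active arm, report the reasons for any shortfall, and state that it is not evidence of dose-response.

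State in Item 6 whether participants who stop early have a second scan, and reconcile the session number with the pulse total.

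The cost is a wording change and one fewer named test for a mechanistic aim. No new scans or participants are needed.
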